1 PROTOCOL SUMMARY

1.1 Schedule of activities (SoA)

The procedures for the Screening and Treatment Periods in this study are presented in Table 1, and the procedures for the Follow-up Period are presented in Table 2.

Whenever vital signs and blood draws are scheduled for the same nominal time, the assessments should occur in the following order: vital signs and then blood draws. The timing of the vital signs assessments should be such that it allows the blood draw (eg, pharmacokinetic (PK) blood sample) to occur at the timepoints indicated in the Schedule of Activities (SoAs). Whenever electrocardiograms (ECGs), vital signs, and blood draws are scheduled for the same nominal time, the assessments should occur in the following order: ECG, vital signs, and then blood draws. The timing of the first 2 assessments should be such that it allows the blood draw (eg, PK blood sample) to occur at the timepoints indicated in the SoAs. Safety assessments must be done prior to dosing.

For durvalumab monotherapy / placebo treatment

- Participants may delay dosing under certain circumstances.
 - Dosing may be delayed per the Dosing Modification and Toxicity Management Guidelines, due to either an immune or a non-immune-related adverse event (AE).
 - If dosing must be delayed for reasons other than treatment-related toxicity, dosing will resume as soon as feasible.
 - Dosing intervals of subsequent cycles may be shortened as clinically feasible in order to gradually align treatment cycles with the schedule of tumour efficacy (Response Evaluation Criteria in Solid Tumors [RECIST]) and patient-reported outcome (PRO) assessments. Subsequent time between 2 consecutive doses cannot be less than 21 days, based on the half-life of durvalumab (see current Investigator Brochure [IB] for durvalumab).
- If a participant has a delay to an infusion of study treatment, all tumour efficacy assessments should still be conducted relative to date of randomisation, and PRO assessments should be conducted relative to the date of Cycle 1 Day 1 visit date (i.e. date of randomization/first dose).

Table 1Schedule of activities for durvalumab/placebo treatment

	Screening Visit Part I	Screening Visit Part II	C1	C2	C3	C4	C5 to PD	
Week	-12 to -1	-4 to -1	0	q4w ±3	3 days unless dos	sing needs to be h	eld for toxicity reasons	For details,
Day	-84 to -1	-28 to -1	1 ^b	q28d ±.	3 days unless do	sing needs to be l	held for toxicity reasons	see Section
Informed consent								·
Informed consent: tumour sample collection ^c (part I screening ICF)	X							5.1
Informed consent: study procedures ^c (part II screening ICF)		Х						5.1
Study procedures						•		·
Physical exam (full)		Х						8.2.2
Targeted physical exam (based on symptoms)			Х	Х	X	X	Х	8.2.2
Vital signs		Х	Х	Х	Х	Х	Х	8.2.3
Weight		Х	Х	Х	Х	X	Х	8.2.3
ECG ^d		Х			As clin	nically indicated		8.2.4
Concomitant medications		<					>	6.4
Demography	X							5.1
Tobacco use		Х						5.1
Eligibility criteria	Х	Х	Х					5.1, 5.2
Randomisation			Х					6.2
Laboratory assessments								
Clinical chemistry ^e		Х	X ^f	Х	Х	Х	Х	Table 7
Haematology ^e		Х	\mathbf{X}^{f}	Х	Х	Х	Х	Table 8

	Screening Visit Part I	Screening Visit Part II	C1	C2	C3	C4	C5 to PD	
Week	-12 to -1	-4 to -1	0	q4w ±3	days unless dos	ing needs to be l	held for toxicity reasons	For details,
Day	-84 to -1	-28 to -1	1 ^b	q28d ±3	3 days unless dos	sing needs to be	held for toxicity reasons	see Section
Coagulation		Х			As clir	nically indicated		Table 9
TSH (reflex free T3 or free T4 ^g)		Х	X ^h	Х	Х	Х	Х	Table 7
Urinalysis		Х			As clir	nically indicated		Table 10
Hepatitis B and C and HIV		Х						8.2.6
Pregnancy test ^{ij}		Х	Х	Х	Х	Х	Х	8.2.1
Pharmacokinetics								
CCI								8.5
Monitoring								
WHO/ECOG performance status		Х	х	X	x	х	Х	8.2.5
AE/SAE assessment ¹		<					>	8.3
IP administration								
Durvalumab (monotherapy)/placebo ^m			Х	Х	X	Х	Х	6.1.1.1, 6.1.2.1
Other assessments and assays					•			
CCI						j		8.5
CCI								8.8.2
CCI								8.8.2

	Screening Visit Part I	Screening Visit Part II	C1	C2	C3	C4	C5 to PD	
Week	-12 to -1	-4 to -1	0	q4w ±3	$q4w \pm 3$ days unless dosing needs to be held for toxicity reasons			
Day	-84 to -1	-28 to -1	1 ^b	q28d ±3	For details, see Section			
EORTC QLQ-C30, QLQ-LC13, and EQ-5D-5L ⁿ			х	q4w (±1 week) for the first 8 weeks (relative to the date of Cycle 1 Day 1 visit date i.e. date of randomization/first dose), q8w(±1 week) thereafter until the 48th week (relative to the date of Cycle 1 Day 1 visit date i.e. date of randomization/first dose), and then q12w(±1 week) thereafter until confirmed PD by RECIST 1.1 by investigational site review				8.1.4
Health resource use (HOSPAD)			Х	Х		Х	Х	8.9
CCI								8.8.1
CCI								6.2.1
Efficacy evaluations		-						
Tumour assessments (CT or MRI) (RECIST 1.1) ^p		Х	the def confir sch	On-study tumour assessments occur $q8w \pm 1$ week for the first 48 weeks (relative to the date of randomisation) and then $q12w \pm 1$ week thereafter until RECIST 1.1-defined radiological progression plus 1 or more additional follow-up scans for confirmation of progression until confirmed radiological progression. The on-study schedule of $q8w \pm 1$ week (relative to the date of randomisation) for the first 48 weeks and then $q12w \pm 1$ week thereafter MUST be followed regardless of any delays in dosing.				8.1

a A newly acquired sample ≤ 3 months old is preferred, but an archived sample ≤6 months old is acceptable (refer to lab manual for detail about sample age requirements). A biopsy procedure during screening period is not allowed. Newly acquired or archived tumour sample must be obtained before CRT. Any irradiated sample is not acceptable.

^b Every effort should be made to minimise the time between randomisation and starting treatment (i.e. within 3 days of randomisation).

^c Written informed consent and any locally required privacy act document authorisation must be obtained prior to performing any protocol-specific procedures, including screening/baseline evaluations. Part I Screening: all participants will be required to provide informed consent to supply their tumour samples (archived or newly acquired) for entry into this study. A biopsy procedure during screening period is not allowed, and an irradiated sample is not acceptable. Part II screening ICF must be signed after participants complete CRT. Part I screening ICF needs to be signed prior to (or at the same time as) signature of the Part II screening ICF. The collection of additional biopsies upon progression is strongly encouraged. If laboratory or imaging procedures were performed for alternate reasons prior to signing inform consent of study

Clinical Study Protocol - 6.0 Durvalumab

procedures, these can be used for screening purposes with consent of the participant. However, all screening laboratory and imaging results must have been obtained within 28 days of randomisation.

- ^d Any clinically significant abnormalities detected require triplicate ECG results.
- ^e Serum or plasma clinical chemistry (including LFT monitoring), haematology, and coagulation parameters may be performed more frequently if clinically indicated.
- ^f If part II screening clinical chemistry, haematology, and coagulation parameter assessments are performed within 3 days prior to Day 1 (first infusion day), they do not need to be repeated at Day 1.
- ^g Free T3 or free T4 will only be measured if TSH is abnormal or if there is clinical suspicion of an AE related to the endocrine system.
- ^h If TSH is measured within 14 days prior to Day 1 (first infusion day), it does not need to be repeated at Day 1.
- For women of childbearing potential only. A urine or serum pregnancy test is acceptable. Women of childbearing potential are required to have a pregnancy test within 7 days prior to the first dose of study treatment and then q4w. Pregnancy test may occur on Day 1, but results must be available and reviewed by the treating physician or Investigator prior to commencing an infusion.
- ^j Pre-dose same day as infusion
- ^k Within 10 minutes of the end of infusion.
- ¹ For AEs/SAEs reported during part II screening, additional information such as medical history and concomitant medications may be needed
- ^m Results for haematology, LFTs, electrolytes, and creatinine must be available before commencing an infusion (within 3 days) and reviewed by the treating physician or Investigator prior to dosing.
- ⁿ Will be administered using a site-based electronic device. It is preferred that PRO questionnaires are completed prior to any other study procedures (following informed consent) and before discussion of disease progression to avoid biasing the participant's responses to the questions.
- ^o Documented EGFR and ALK status obtained from local lab uses a well-validated, local regulatory-approved kit is acceptable. EGFR and ALK status may also be tested in central lab at screening part I visit, if there's no available documentation of EFGR and ALK status from local lab.
- ^p Tumor assessment will be performed on images from CT (preferred) or MRI, each preferably with iv contrast, of the chest and abdomen (including the entire liver and both adrenal glands). Additional anatomy, e.g. pelvis, should be imaged based on signs and symptoms of individual participants at Baseline and follow-up. If a participant's scan is assessed as a RECIST 1.1-defined radiological progression, a follow-up scan for confirmation of the prior radiological progression is collected no earlier than 4 weeks after and no later than the next regularly scheduled imaging visit after the prior RECIST 1.1-defined PD, and this scan is evaluated using the confirmation of radiological progression criteria outlined in Appendix E. If the subsequent scan confirms the immediate prior radiological PD, no additional scans are required; however, if the subsequent scan does not confirm the immediate prior radiological PD, scanning should continue on the original imaging visit schedule until the next clinical progression/deterioration or RECIST 1.1-defined PD, which in turn will require a subsequent scan evaluated using confirmation of radiological progression criteria outlined in Appendix E. If an unscheduled assessment was performed and the participant has not progressed, every attempt should be made to perform the subsequent assessments at their next regularly scheduled visit. See Section 6.1.3 and Section 8.1 for additional details relevant to tumour assessment.
- Note: All assessments on treatment days are to be performed prior to infusion, unless otherwise indicated.

ADA Anti-drug antibody; AE Adverse event; ALK Anaplastic lymphoma kinase; C Cycle; CT Computed tomography; ECG Electrocardiogram; ECOG Eastern Cooperative Oncology Group; EGFR Epidermal growth factor receptor; EORTC QLQ-C30 European Organisation for Research and Treatment of Cancer 30-item core quality of life questionnaire; HIV Human immunodeficiency virus; ICF Informed consent form; IP Investigational Product; iv Intravenous; LFT Liver function test; miRNA Micro ribonucleic acid; MRI Magnetic resonance imaging; mRNA Messenger ribonucleic acid; NSCLC Non-small cell lung cancer; PD Progression of disease; PD-L1 Programmed death ligand 1; PK Pharmacokinetic; q4w Every 4 weeks; q8w Every 8 weeks; q12w Every 12 weeks; q28d Every 28 days; QLQ-LC13 13-item self-administered questionnaire for lung cancer; RNA Ribonucleic acid; SAE Severe Adverse Event; RECIST Response Evaluation Criteria in Solid Tumors; T3 Triiodothyronine; T4 Thyroxine; TSH Thyroid-stimulating hormone; WHO World Health Organization; WT Body weight.

AstraZeneca

	Time since last dose of IP								
	Day (±3)			12 months					
Evaluation	30	2	3	4	6	8	10	then every 2 months (±2 weeks) ^a	For details, see Section
EORTC QLQ-C30, QLQ-LC13, and EQ-5D-5L as well as health resource use (HOSPAD) ^b	Participant questionnaires and information related to health resource use should be completed relative to the date of Cycle 1 Day 1 visit date(i.e. date of randomization/first dose) as follows: $q4w$ (± 1 week) for the first 8 weeks, every 8 weeks ± 1 week thereafter for the first 48 weeks (per Table 1), then every 12 weeks ± 1 week thereafter until PFS2.								
Physical examination (full)	Х								8.2.2
Vital signs (temperature, respiratory rate, blood pressure, and pulse)	Х								8.2.3
Weight	Х	X	X						8.2.3
Pregnancy test ^c	X As clinically indicated						8.2.1		
AE/SAE assessment	Х	X	X						8.3
Concomitant medications	Х	X	X						6.4
WHO/ECOG performance status	At timepoints consistent with tumour assessments; at 30, 60, and 90 days after treatment discontinuation; and then at initiation of subsequent anticancer therapy ^d							8.2.5	
Subsequent anticancer therapy ^e and second progression assessment ^{f, g}	<>					8.1			
Survival status ^h		X	X	Х	X	X	Х	X	8.1.2
Haematology	Х	X	X						Table 8
Clinical chemistry	Х	X	X						Table 7
TSH (reflex free T3 or free T4 ⁱ)	Х	X	X						Table 7
PK assessment			Х						8.5

Table 2Schedule of activities for participants who have discontinued treatment with durvalumab /placebo

	Time since last dose of IP								
	Day (±3)	±3) Months (±1 week)						12 months	
Evaluation	30	2	3	4	6	8	10	then every 2 months (±2 weeks) ^a	For details, see Section
CCI									8.5
Tumour assessment (CT or MRI) (RECIST 1.1) ^j	On-study tumour assessments occur $q8w \pm 1$ week for the first 48 weeks (relative to the date of randomisation) and then $q12w \pm 1$ week thereafter until RECIST 1.1-defined radiological progression plus 1 or more additional follow-up scans for confirmation of progression until confirmed radiological progression, the end of study, death, study discontinuation, or Sponsor decision (whichever comes first). The on-study schedule of $q8w \pm 1$ week (relative to the date of randomisation) for the first 48 weeks and then $q12w \pm 1$ week thereafter MUST be followed regardless of any delays in dosing. Additional scans to be completed per standard practice post-progression.							8.1	

Participants on Survival Follow-up at the time of final DCO for the study will be considered to have completed the study and will continue to receive treatment per local standard of care.

- ^b Will be administered using a site-based electronic device. It is preferred that PRO questionnaires are completed prior to any other study procedures and before discussion of disease progression to avoid biasing the participant's responses to the questions.
- ^c For women of childbearing potential only. A urine or serum pregnancy test is acceptable.
- ^d WHO/ECOG performance status should also be collected at other study site visits that the participant attends, if appropriate study site staff are available to collect such information. In addition, WHO/ECOG performance status should be provided when information on subsequent anticancer therapy is provided, where possible.
- e Details of any treatment for NSCLC (including surgery) after the last dose of IP must be recorded in the eCRF. At minimum, collect the start date and description of the subsequent anticancer therapy.
- ^f Following the first progression event used for the primary variable, PFS (the first progression), the site will be asked on a regular basis (q8w ±1 week for the first 48 weeks [relative to the date of randomisation], and then q12w ±1 week) if the participant has had a second progression event. Actual timing of assessments for a second progression event will be according to local standard practice. PFS2 assessment will be performed by the Investigator and defined according to local standard clinical practice and may involve any of the following: objective radiological imaging, symptomatic progression, or death. (The follow-up scan confirming an immediate RECIST 1.1-defined radiological progression is not to be considered as the second progression.)
- ^g For participants who discontinue their assigned IP following progression, available readings of CT/MRI from local practice will be collected from participants` medical charts whilst information on subsequent anticancer treatment and/or PFS2 is collected.
- ^h Participants may be contacted in the week following DCOs to confirm survival status. Details of any treatment for NSCLC (including surgery) post the last dose of IP must be recorded in the eCRF. Participants who decline to return to the study site for evaluations should be contacted by telephone as indicated in the SoAs as an alternative.
- ⁱ Free T3 or free T4 will only be measured if TSH is abnormal or if there is clinical suspicion of an AE related to the endocrine system.
- ^j See Section 6.1.3 and Section 8.1 for additional details relevant to tumour assessment.

ADA Anti-drug antibody; AE Adverse event; C Cycle; CT Computed tomography; DCO Data cutoff; ECOG Eastern Cooperative Oncology Group; eCRF Electronic case report form; EORTC QLQ-C30 European Organisation for Research and Treatment of Cancer 30-item core quality of life questionnaire; EQ-5D-5L EuroQoL 5-dimension, 5-level health state utility index; IP Investigational Product; MRI Magnetic resonance imaging; NSCLC Non-small cell

AstraZeneca

lung cancer; PD Progression of disease; PFS2 Time from randomisation to second progression; PK Pharmacokinetic; q8w Every 8 weeks; q12w Every 12 weeks; QLQ-LC13 13-item self-administered questionnaire for lung cancer; SAE Severe Adverse Event; RECIST Response Evaluation Criteria in Solid Tumors; T₃ Triiodothyronine; T₄ Thyroxine; TSH Thyroid-stimulating hormone; WHO World Health Organization

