Clinical Study Protocol							
Drug Substance	Durvalumab						
Study Code	D933YC00001						
Version	6.0						
Date	28 Aug 2023						

A Phase III, Randomised, Double-Blind, Placebo-Controlled, Multicentre Study of Durvalumab as Consolidation Therapy in Patients with Locally Advanced, Unresectable, Non-Small Cell Lung Cancer (Stage III) Who Have Not Progressed following Definitive, Platinum-Based, Chemoradiation Therapy (PACIFIC 5)

Sponsor: AstraZeneca AB, [name]

Regulatory Agency Identifying Number(s):

EudraCT number 2018-002294-22

VERSION HISTORY

Version 6.0, 28 August 2023

All Sections

Updated "patient" to "participant" as per latest template.

Section 1.1 – SoA, Section 4.1 – Overall design, 7.1.1 – Procedures for discontinuation of study treatment and Section 8.1.2 – Survival assessments

- Revised visit frequency from every 6 months to every 2 months in the table header of SoA Table 2 "Schedule of activities for participants who have discontinued treatment with durvalumab /placebo" to be consistent with the survival follow-up frequency and updated the wording in Section 8.1.2 for clarification.
- Clarified participants who permanently discontinue drug for reasons other than objective RECIST 1.1 disease progression should continue to have RECIST 1.1 scans regardless of whether or not the participants started a subsequent anticancer therapy.

Section 1.2 – Synopsis and Section 9.6 –Interim analyses

Removed IDMC review of unblinded OS interim analysis.

Section 6.1.3 - Duration of treatment and Section

Added the clarification that participants in placebo arm will no longer receive any further placebo treatment after the study unblinded.

Section 6.2.4 – Methods for ensuring blinding

Specified the blinding of assigned study treatment will remain until final analysis of PFS.

Section 4.4 – End of study definition,6.1.3 – Duration of treatment and Section 6.6 – Treatment after the end of the study,

Moved the relevant information on participant/study data management post final DCO and study completion in Section 4.4 and Section 6.1.3 to Section 6.6 for consolidation.

Section 7.2 - Lost to follow-up

Specified how to perform patient follow-up when onsite visit is not applicable.

Section 7.3 – Withdrawal from the study

Updated the description of participant withdraw from the study per CSP template.

Section 8.3 - Collection of adverse events

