During the Treatment Period, participants who are clinically stable at an initial Response Evaluation Criteria in Solid Tumors 1.1-defined radiological progression of disease may continue to receive study treatment at the discretion of the Investigator and participants. A follow-up scan is to be collected after the initial Response Evaluation Criteria in Solid Tumors 1.1-defined radiological progression of disease, no less than 4 weeks after the prior assessment of progression of disease and no later than the next regularly scheduled imaging visit, and this scan is evaluated using the Confirmation of Radiological Progression criteria outlined in Appendix E. Participants with confirmed PD who continue to receive study treatment at the discretion of the Investigator and participant (following consultation with AstraZeneca) can receive treatment until no longer having clinical benefit, and tumor
assessments should continue on their regular imaging schedule for the duration of treatment. If the subsequent scan does not confirm the immediate prior radiological progressive disease, scanning should continue until the next Response Evaluation Criteria in Solid Tumors 1.1defined radiological progression of disease, which in turn will require a subsequent scan evaluated using the Confirmation of Radiological Progression criteria outlined in Appendix E.

Follow-up of participants post discontinuation of study treatment

Participants who have discontinued study treatment due to toxicity or symptomatic deterioration, clinical progression, or who have commenced subsequent anticancer therapy will be followed up with tumour assessments until Response Evaluation Criteria in Solid Tumors 1.1-defined radiological progression of disease plus an additional follow-up scan or until death (whichever comes first) and followed for survival. PRO questionnaires will be followed up until PFS2.

Survival

All participants randomised in the study should be followed up for survival.

Independent Data Monitoring Committee:

The Independent Data Monitoring Committee will meet periodically in accordance with the IDMC charter to review safety assessments and make recommendations to continue, amend, or stop the study based on safety findings.

Full details of the Independent Data Monitoring Committee procedures and processes can be found in the Independent Data Monitoring Committee Charter.

Statistical methods

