8.1.4 Clinical outcome assessments

A Clinical Outcome Assessment (COA) is any assessment that may be influenced by human choices, judgement, or motivation and may support either direct or indirect evidence of treatment benefit. Patient Reported Outcomes (PROs) is one of the types of COAs. PROs is an umbrella term referring to all outcomes that are directly reported by the participant. The following PRO instruments will be administered in this study: EORTC QLQ-C30 v3 (core questionnaire), EORTC QLQ-LC13 (lung cancer module), and EQ-5D-5L; see Appendix G.

Timings of the assessments for PRO are presented in Table 1 (Screening and the Treatment Period) and Table 2 (Follow-up).

If participants have scans at an outside facility or missed a scheduled data collection, PRO questionnaires need to be administered at the next visit.

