3.2.3 Patient-reported outcomes (PRO)

Symptoms and overall quality of life (QoL) will be assessed using the PRO questionnaires, European Organisation for Research and Treatment of Cancer (EORTC) 30-item core (QoL) questionnaire (QLQ-C30) ([Aaronson et al 1993](#)) and 13-item lung cancer QoL questionnaire (QLQ-LC13) ([Bergman et al 1994](#)) (secondary endpoints). All questionnaires will be scored according to published guidelines or the developer's guidelines, if published guidelines are not available. All PRO data will be collected until PFS2.

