8 APPENDIX

APPENDIX A. 2 MISSED VISITS

ePRO Assessments

As per Section 3.2.3.1, confirmation of deterioration/worsening will first be determined, then the censoring rules will be applied. For ePRO assessments, we will apply a ‘look-forward’ approach to the 2 missed visit rule.

For example:

Baseline	V1	V2	V3	V4	V5	V6	V7	V8	Observed confirmed deterioration visit*	Time to Deterioration derivation
	NC	DT	DT	NC	MV	NC	IMP	NC	Event at V2	Event at V2
	MV	MV	NC	DT	MV	DT	DT	NC	Event at V4	No event, censor at baseline
	MV	DT	NC	MV	MV	DT	DT	NC	Event at V6	No event, censor at V3
	NC	DT	NC	MV	IMP	DT	NC	DT	Event not confirmed, but if last DT then confirmed	Event at V8

	NC	DT	NC	MV	IMP	DT	MV	DT	Event at V6	Event at V6
	NC	IMP	NC	IMP	MV	MV	IMP	DT	Event at V8, last DT	No event, censor at V4
	MV	MV	NC	MV	MV	DT	DT	NC	Event at V6	No event, censor at baseline
	NC	DT	MV	MV	DT	NC	IMP	DT	Event at V2	Event at V2

DT Deterioration; IMP Improvement; MV Missed visit; NC No change (/stable).

*Missed visits are allowed in between assessments confirming deterioration/worsening, and confirmation of deterioration/worsening requires at least 14 days between assessments.

Length of 2 missed visit window for EORTC QLQ-C30 and QLQ-LC13

The scheduled visit assessments and visit windows for the QLQ-C30 and QLQ-LC13 are every 4 weeks (± 1 week) for the first 8 weeks from randomization, and then every 8 weeks (± 1 week) up to 48 weeks relative to date of randomization, and then every 12 weeks (± 1 week) until confirmed PD by RECIST 1.1 per Investigator assessment, and then every 12 weeks (± 1 week) thereafter until PFS2.

Missing baseline or within 2 visits of baseline:

- A patient without baseline will be censored at day 1 unless they die \leq day 63.
- Any assessment \leq day 63 is within 2 visits (2×4 weeks + 1 week) of baseline and therefore cannot be censored for missing visits.

Schedule: q4w ± 1 week:

For any assessment $>$ day 1 then visit schedule is q4w ± 1 week and thus the maximum time between 2 consecutive assessments is $7+28+28+7=70$ days.

Schedule: q8w ± 1 week:

- For any assessments where the visit schedule changes from q4w ± 1 week to q8w ± 1 week, the maximum time between 2 consecutive assessments is $7+28+56+7 = 98$ days.
- For any assessments where the visit schedule is q8w ± 1 week, the maximum time between two consecutive assessments is $7+56+56+7 = 126$ days.

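### Participants treated beyond confirmed PD have no protocol-scheduled PRO questionnaires until treatment stops, although the SAP assumes collection to PFS2

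*Protocol*

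**What the plan says.** Protocol 8.1.4 takes the timing of PRO assessments from two tables only: Table 1 for screening and treatment, and Table 2 for follow-up.

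- **Table 1.** The questionnaire row is every 4 weeks to week 8, every 8 weeks to week 48, then every 12 weeks "thereafter until confirmed PD by RECIST 1.1 by investigational site review".
- **Table 2.** It has the same grid, counted from Cycle 1 Day 1, but continues "thereafter until PFS2". Its title is "Schedule of activities for participants who have discontinued treatment with durvalumab /placebo", and under Section 7.1.1 participants enter follow-up on permanent discontinuation of IP.
- **Treatment after confirmed PD.** The Synopsis (progression during treatment) and Section 6.1.3 provide for "Participants with confirmed PD who continue to receive study treatment at the discretion of the Investigator and participant", following consultation with the sponsor and for as long as there is clinical benefit. For that time they say that the tumour "assessments should continue on their regular imaging schedule for the duration of treatment". They do not mention questionnaires.
- **SAP.** Section 3.2.3 says "All PRO data will be collected until PFS2". Appendix A describes the questionnaires as running "until confirmed PD by RECIST 1.1 per Investigator assessment, and then every 12 weeks" to PFS2. Neither place makes an exception for participants still on treatment.

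**The concern.** A participant who has confirmed PD and stays on study treatment has left the Table 1 questionnaire row and has not yet entered Table 2. A participant who stops treatment at the same PD goes on completing forms.

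The schedule itself therefore creates missing data, and in a selected group: those judged still to be benefiting. The planned MMRM uses data to 12 months and relies on missingness being explained by what is in the model. Neither progression nor continued treatment is in it. Time to deterioration has a two-missed-visit rule that can move a later event back to a censoring time before the gap. Symptoms and HRQoL are a secondary objective, and EQ-5D-5L is exploratory.

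**Working it through.** **1. Which rule governs each state**

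| State | Governing text | Questionnaires scheduled by the Protocol |
|---|---|---|
| On treatment, before confirmed PD | Table 1 | Yes: weeks 4, 8, 16, 24, 32, 40, 48, then every 12 weeks |
| On treatment, after confirmed PD | Synopsis and 6.1.3 | None: Table 1 row has ended, Table 2 has not begun |
| Off treatment, before PFS2 | Table 2 | Yes: same grid, to PFS2 |

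**2. Is the middle row inside the period the SAP treats as covered?** Normally yes. SAP 3.2.2.7 requires both a first progression and subsequent anticancer therapy before a second progression can count. Protocol 7.1 ends IP when alternative anticancer therapy starts. A living participant still on IP has therefore normally not reached PFS2.

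**3. Forms not scheduled.** The documents give no duration of treatment after confirmed PD, so these cases are assumed.

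| PD confirmed | Treated to | Table 1 | Table 2 grid | Every 12 weeks from PD |
|---|---|---|---|---|
| Week 24 | Week 48 | 0 | 3 (weeks 32, 40, 48) | 2 |
| Week 24 | Week 72 | 0 | 5 | 4 |
| Week 60 | Week 84 | 0 | 2 | 2 |

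With PD confirmed at weeks 16 to 60 and 8 to 48 further weeks on treatment, Table 1 always gives 0, the Table 2 grid gives 0 to 5, and a 12-week schedule from PD gives 0 to 4.

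**4. Two-missed-visit limits in SAP Appendix A.** Its figures reproduce:

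- every 4 weeks: 7 + 28 + 28 + 7 = 70 days
- change from 4 to 8 weeks: 7 + 28 + 56 + 7 = 98 days
- every 8 weeks: 7 + 56 + 56 + 7 = 126 days
- change from 8 to 12 weeks: 7 + 56 + 84 + 7 = 154 days
- every 12 weeks: 7 + 84 + 84 + 7 = 182 days

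**5. Does a gap exceed the limit?** Take a last form at week 24 (day 7 × 24 + 1 = 169), treatment continuing past week 40, and the next form at week 48 (day 7 × 48 + 1 = 337). The gap is 337 − 169 = 168 days. That exceeds 126 and 154 but not 182. Appendix A does not say whether the 8-week grid continues after a PD confirmed before week 48 or changes to 12 weeks at PD. The same participant is censored on one reading and not on the other.

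After week 48 both readings give 12-week intervals. With PD confirmed at week 60, treatment past week 84 and the next form at week 96, the gap is (96 − 60) × 7 = 252 days, above 182. That case needs more than 24 further weeks on treatment.

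**6. Compliance.** SAP 3.2.3.2 decides whether a progressed participant is still under PRO follow-up by the later of progression and safety follow-up. For someone still on treatment, safety follow-up has not ended. Forms in the gap can therefore count as expected although the Protocol does not schedule them. The same rule also differs from collection to PFS2.

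**The case against.** The strongest reply is that treatment after confirmed PD is an exception. Several sections set treatment to run until confirmed radiological progression, and Protocol 7.1 lists confirmed progression among the reasons for giving no further IP. That sentence can be read as confirmed PD alone, or as confirmed PD together with a judgement of no benefit. The last treatment column of Table 1 is itself headed to PD. On this view the affected group is tiny or empty, the gap closes when IP stops, and the PRO endpoints lie outside the multiple testing procedure (Protocol 9.1).

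Most of this stands as a limit on size. It does not remove the gap, because the Synopsis and 6.1.3 expressly provide for treatment after confirmed PD. It also shows that the PRO row is one symptom of a wider mismatch: Section 7.1 and those two passages must be reconciled, and no position is taken here on which treatment rule is right.

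Two other replies are weaker. The Synopsis does say that questionnaires run to PFS2, but in the paragraph on participants who have discontinued study treatment. SAP Appendix A does describe forms after confirmed PD, but a SAP does not instruct sites, so it shows the mismatch without curing it. The scan row of Table 1 also ends at confirmed progression. The text on continued treatment repairs that for scans and not for questionnaires, which suggests an oversight.

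**Conclusion.** The gap is real in the text: a participant kept on study treatment after confirmed PD has no protocol-scheduled questionnaire until treatment stops, inside a period the SAP treats as covered. It rests on the Synopsis and 6.1.3 meaning what they say about treatment after confirmed PD. The number affected is unknown and probably small. PFS and OS are untouched.

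Three stronger conclusions are tempting and not supported:

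- A reader might infer that a later deterioration is always censored at the form before the gap. That depends on how long treatment continues and, before week 48, on which schedule Appendix A intends.
- A reader might infer a bias of some number of points on the symptom scales. The documents give neither the share treated beyond confirmed PD nor their scores. The planned estimate is a between-arm average over visits to 12 months, not a mean after progression, so no size can be stated.
- A reader might infer that PRO data after progression are lost for good. Table 2 restarts them once IP stops.

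**What to change.** In the Table 1 questionnaire row, replace "thereafter until confirmed PD by RECIST 1.1 by investigational site review" with "thereafter until PFS2", on the same grid as Table 2.

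The SAP needs matching changes:

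- Appendix A should state which grid, and so which missed-visit limit, applies after a PD confirmed before week 48.
- The expected-questionnaire rule in 3.2.3.2 should use PFS2 in place of the later of progression and safety follow-up.

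Separately, reconcile Protocol 7.1 with the Synopsis and 6.1.3 on whether study treatment may continue after confirmed PD.

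The cost is a protocol amendment and a SAP amendment, plus a few more questionnaire sessions of about 10 minutes each (Protocol 8.1.4.3) at visits these participants already attend for dosing.
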